4.4 Treatments

This is a single-arm registry study, so there are no treatments groups

4.4.1 Treatment Groups

This is not applicable for the single arm observational study.

4.4.2 Randomization

This is not applicable for the single arm observational study.

4.5 Control to Minimize Bias

The following measures will be taken to minimize and/or avoid bias in this registry:

- a) A multi-center observational registry design is used to help ensure a representative sample of physicians performing the procedure and to provide a reasonable enrollment period.
- b) Sites will have the ability to represent all-comers in various percutaneous cardiac intervention procedures.
- c) Subjects will be screened to confirm study eligibility with defined inclusion/exclusion criteria prior to inclusion. Sites are required to maintain a log of all subjects screened and enrolled for the study.
- d) Data collection requirements and study procedures will be standardized across all sites. All sites will follow the same version of the protocol and eCRFs.
- e) Collection and archiving of image data will be managed adequately to reduce the impact of data loss and error in analysis.
- f) Standardized protocol training will be developed and distributed to all participating sites to ensure data of uniform quality are obtained from all subjects
- g) Regular monitoring will be conducted to verify source data and adherence to the protocol

Document ID:	ICE VeriSight Registry SAP	Document title:	Classification:	For internal use
		Statistical Analysis Plan		
Modified:	02SEP2022		Author:	[name]
Version:	1.0	User Tool ID:	Approver:	[name]
Status:	Final	User Tool Version Date:	Page:	8 of 16

Statistical Analysis Plan

5 EFFICACY AND SAFETY VARIABLES

The overall purpose of this observational multi-center registry is to report real-world performance (efficacy) and safety of VeriSight ultrasound guided ICE imaging in percutaneous cardiac intervention procedures when used in standard clinical practice.

5.1 Efficacy and Safety Measurements

See Sections 5.3 below.

5.2 Appropriateness of Measurements

Please refer to section 5.3 and 5.4 below

5.3 Efficacy Variables

5.3.1 Primary Efficacy Variables

- a) **Technical success** – defined by successful delivery of VeriSight to the target intracardiac position and sustained device operation during the procedure

Successful device delivery is defined as ability of the VeriSight catheter to reach the target intracardiac anatomical position. Sustained operation of VeriSight is absence of technical complications or procedural delays/ disruption.
- b) **Imaging success** – Adequate image quality as determined by the investigator using a Likert scale assessment.
- c) **Clinical success** - Adequacy of VeriSight imaging for visualization of major cardiac structures, and guiding procedural intervention, and ability to detect/ assess intra-procedural complications. Clinical success will be measured by ability of VeriSight to adequately guide procedural intervention using the 4 parameters listed below:
 - number of great vessels imaged, number of chambers imaged, including angle of views, axis, and modality
 - assessment of key cardiac structures and sizing relevant anatomy
 - verification of delivery and/or placement of interventional device (e.g. trans septal puncture devices, closure devices (LAAO, PFO, ASD, VSD), valves (e.g for TAVR), clip devices (e.g. mitral clip), annuloplasty devices (e.g. Cardioband), ablation devices (e.g cryoballoon, RF ablation catheter), leads (leads extraction), etc.)

Document ID:	ICE VeriSight Registry SAP	Document title:		Classification:	For internal use
		Statistical Analysis Plan			
Modified:	02SEP2022			Author:	[name]
Version:	1.0	User Tool ID:	16.2.6UserTool0025	Approver:	[name]
Status:	Final	User Tool Version Date:	29Oct2019	Page:	9 of 16

Statistical Analysis Plan

- assessment of procedural related complication (e.g. cardiac tamponade, pericardial effusion, thrombus) will be documented for each patient based on the procedure type.

5.3.2 Secondary Efficacy Variables

Secondary analyses will include the following:

- a) Procedural characterization when using VeriSight measured by
 - i. type of procedure utilizing ICE imaging
 - ii. total procedural room time (door-in to door-out, mins), total procedure time (skin to skin, mins)
 - iii. total fluoroscopy time (mins)
 - iv. total contrast volume used (cc), fluoroscopic dosage (mGy)
 - v. ability to image from the right side of the heart for a left sided intervention
 - vi. TEE usage rate and avoidance of TEE procedure
 - vii. Other imaging modality used during the procedure
 - viii. Change in management from use of VeriSight – need for high risk patient and/or procedure management
 - ix. Duration and type of anesthesia
 - x. Freedom from general anesthesia
- b) Device characterization when using VeriSight based on a scoring scale for the physical attributes of the VeriSight catheter
- c) Physician survey regarding the Philips ICE using a five-point ordinal Likert-type rating scale
- d) Staff survey regarding the Philips ICE using a five-point ordinal Likert-type rating scale

5.4 Safety Variables

Device related adverse events periprocedural through discharge or 48 hours post-procedure, whichever is earlier.

Document ID:	ICE VeriSight Registry SAP	Document title:		Classification:	For internal use
		Statistical Analysis Plan			
Modified:	02SEP2022			Author:	[name]
Version:	1.0	User Tool ID:	16.2.6UserTool0025	Approver:	[name]
Status:	Final	User Tool Version Date:	29Oct2019	Page:	10 of 16

Statistical Analysis Plan

6 ENDPOINT DEFINITION

The statistical endpoint is a registry trial outcome value that is measured for each subject, for example subject is a success for binary endpoint.

The four key endpoints are:

1. Binary end points are yes/no type of measurements.
2. Categorical endpoints are categorized measurements such as race, gender. Typical summary measures are frequencies and percentages.
3. Continuous endpoints are measured on a numerical scale such as age in years and heights in inches. Typical summary measures are N, mean, median, standard deviation.
4. Time to event endpoints.

7 DATA QUALITY ASSURANCE

Each site, both clinical and laboratory (if applicable), should have SOPs for quality management that describe:

- How data will be evaluated for compliance with the protocol, ethical standards, regulatory compliance, and accuracy in relation to source documents.
- The documents to be reviewed (e.g., CRFs, clinic notes, questionnaires, audio or video recordings), who is responsible, and the frequency for reviews.
- Who will be responsible for addressing QA issues (e.g., correcting procedures that are not in compliance with protocol) and QC issues (e.g., correcting errors in data entry).
- Staff training methods and how such training will be tracked.
- If applicable, calibration exercises conducted prior to and during the study to train examiners and maintain acceptable intra- and inter-examiner agreement.

Regular monitoring and an independent audit, if conducted, must be performed according to International Conference on Harmonisation-Good Clinical Practice (ICH GCP).

Each clinical site will perform internal quality management of study conduct, data collection, documentation and completion.

Document ID:	ICE VeriSight Registry SAP	Document title:		Classification:	For internal use
		Statistical Analysis Plan			
Modified:	02SEP2022			Author:	[name]
Version:	1.0	User Tool ID:	16.2.6UserTool0025	Approver:	[name]
Status:	Final	User Tool Version Date:	29Oct2019	Page:	11 of 16

Statistical Analysis Plan

Quality control (QC) procedures will be implemented beginning with the data entry system and data QC checks that will be run on the database will be generated. Any missing data or data anomalies will be communicated to the site(s) for clarification/resolution.

8 STATISTICAL METHODS

8.1 Sample Size

A sample size of up to 200 subjects who are scheduled to undergo cardiac interventional percutaneous procedures are planned for the ICE registry and is considered adequate.

No formal statistical hypothesis test is to be performed and the primary and secondary endpoints will also be summarized by descriptive statistics only.

8.2 General Consideration

No formal statistical hypothesis tests are planned. The primarily all data are to be summarized using descriptive statistics only.

The categorical data will be summarized by frequencies and associated percentages. The continuous data will be summarized by appropriate descriptive statistics such as mean, median, mode, standard deviation, and appropriate percentiles.

The response categories, particularly Physician and Staff Survey data, in Likert scales have a rank order, but the intervals between values cannot be presumed equal. Therefore, the mean (and standard deviation) is inappropriate for ordinal data. So, this type of data will be summarized by Percentiles, such as median, proportions, and mode. Display the distribution of data observations in a bar chart.

The exact (Clopper-Pearson) two-sided 95% confidence interval for each of the 3 primary parameters, namely technical success, imaging success, and clinical success will be reported.

The Clopper-Pearson exact method is chosen since it uses exact binomial distribution to provide at least 95% confidence level for the interval for proportions (p) of the three primary efficacy parameters.

8.2.1 Analysis Population

Since registry study is an observational study, no per protocol nor intent-to-treat population analyses is to be performed.

Document ID:	ICE VeriSight Registry SAP	Document title:	Classification:	For internal use
		Statistical Analysis Plan		
Modified:	02SEP2022		Author:	[name]
Version:	1.0	User Tool ID:	Approver:	[name]
Status:	Final	User Tool Version Date:	Page:	12 of 16

Statistical Analysis Plan

8.2.2 Handling of Dropouts or Missing Data

Since this is an observational study, only descriptive statistics are reported, and therefore impact of missing data will not be evaluated.

8.2.3 Efficacy Subset

No subset of efficacy data summarization is planned. Consequently, subset analyses will not be performed.

8.3 Patient Disposition

Enrolled subjects will be followed until discharge or ≤48 hrs post-procedure. A subject is considered to have completed and exited the registry if he or she has completed all phases of the study including the last visit or the last scheduled procedure.

A protocol deviation is defined as an event where the clinical Investigator or site personnel deviate from the registry protocol or study procedures.

8.4 Demographics and Baseline Characteristics

The categorical data will be summarized by frequencies and associated percentages. The continuous data will be summarized by appropriate descriptive statistics such as mean, median, mode, standard deviation, and appropriate percentiles.

8.5 Compliance

This study will be monitored using a risk-based monitoring approach, consistent with the FDA guidance Oversight of Clinical Investigations.

8.6 Concomitant Therapy

Not applicable

8.7 Efficacy Analysis

The categorical data will be summarized by frequencies and associated percentages. The continuous data will be summarized by appropriate descriptive statistics such as mean, median, mode, standard deviation, and appropriate percentiles.

8.7.1 Primary Efficacy Analysis

The exact (Clopper-Pearson) two-sided 95% confidence interval for each of the 3 primary parameters, namely technical success, imaging success, and clinical success will be reported.

Document ID:	ICE VeriSight Registry SAP	Document title:		Classification:	For internal use
		Statistical Analysis Plan			
Modified:	02SEP2022			Author:	[name]
Version:	1.0	User Tool ID:	16.2.6UserTool0025	Approver:	[name]
Status:	Final	User Tool Version Date:	29Oct2019	Page:	13 of 16

Statistical Analysis Plan

The Clopper-Pearson exact method is chosen since it uses exact binomial distribution to provide at least 95% confidence level for the interval for proportions (p) of the three primary efficacy parameters.

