Planned Enrollment	Up to 200 patients scheduled to undergo cardiac interventional percutaneous procedures for which ICE is indicated. Interim analysis is planned after the 100 th patient before further continuity of enrollment in the registry.
Registry Sites	Up to 10 sites in the United States with a maximum enrollment of no more than 30% patients at each participating site
Registry Exit	Either at discharge or ≤48 hours post-procedure, whichever is earlier
Registry Duration	Duration of the registry is estimated to be approximately 24 – 36 months.
Statistical Methodology	No hypothesis testing is planned. All subjects enrolled in the study will be accounted for in the study report. Descriptive statistics and 95% confidence intervals will be calculated for variables.

Document ID:	IGT_IGD_ICE Registry Study_2019_10745	Document title:	Classification:	Confidential	
Modified:	24 APR 2021	Philips ICE Registry			
Version:	2.0	User Tool ID:	16.2.6UserTool0004	Page:	9
Status:	Final	User Tool Version Date	30May2019		

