4.3. Number of Subjects

Enrollment of up to 200 all-comers is planned with distribution across multiple case types such as structural heart disease interventions and electrophysiology procedures. Based on a sample of 100 patients, minimum representation of anticipated enrollment for each procedure type based on investigator survey is the following: minimum of 30 cases for electrophysiology, minimum of 30 cases for left atrial appendage occlusion, minimum of 20 cases for valve intervention, and 5 for ASD/PFO. Each participating registry site will be allowed a maximum enrollment of no more than 30% patients from the total planned enrollment.

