8. DATA ANALYSIS AND STATISTICAL CONSIDERATION

8.1. Sample Size Determination

The sample size of up to 200 subjects was selected based on a goal for the registry to be able to obtain performance and safety associated with use of the VeriSight catheter. This study is observational. Outcomes remain in the exploratory phase, and therefore hypotheses will not be created. Instead, the study will serve to monitor, measure, and evaluate outcomes as a basis for future research. This sample size will provide the opportunity to make proper statistical inference for hypothesis generation. Due to the various procedure types available for use with VeriSight, up to 200 subjects could be enrolled in order to analyze the secondary endpoints by case type.

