4 INVESTIGATION PLAN

4.1 Overall Study Design

This is a prospective, multi-center, observational, single-arm registry intended to gather real-world data to report VeriSight ICE catheter performance and safety. It will be conducted in the United States under the approval of one or more recognized institutional review boards and in compliance with GCP guidelines defined in ISO:14155, the Declaration of Helsinki, and all applicable federal and local laws and regulations. Only on label uses of the VeriSight ICE catheter will be allowed. No specific claims are being validated during this registry, though data analyzed from this registry are intended to inform future claims regarding the performance and safety of the VeriSight catheter.

Enrolled subjects will be imaged with VeriSight for various types of percutaneous cardiac interventional procedures. Enrolled subjects will be followed until discharge or ≤48 hrs post-procedure. The registry has a planned duration of approximately 24-36 months with interim analysis planned at 100 subjects to conduct safety and performance analysis for data submission toward CE mark application. Therefore, the initial analysis (n=100) may be limited in scope and it is anticipated that enrollment will continue beyond 100 patients. Statistical hypotheses are not intended for this registry and descriptive analysis will be conducted.

Data from all clinical sites are intended to be pooled for analysis. It is possible that sub-analyses may be conducted to demonstrate VeriSight guidance for target intervention types in structural heart and electrophysiology procedures (see section 8.9 for examples).

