8.9 Subgroup Analysis

Subgroup analyses reporting of descriptive statistics for demographic, safety and efficacy parameters as requested may be performed for the procedure types obtained from the registry.

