12 TABLES

Statistical summary of analyses will be reported as by appropriate tables which will be provided as a separate document.

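### Are the exact intervals for the three primary success rates too narrow because they leave out variation between sites?

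*SAP*

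**What the plan says.** SAP 8.2 and 8.7.1 plan an exact two-sided 95% interval for each of the three primary success rates, on the ground that the method "uses exact binomial distribution to provide at least 95% confidence level for the interval for proportions". SAP 4.1 and Protocol 8.3 pool the data from all sites.

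On results for parts of the data, SAP 8.2.3 states: "No subset of efficacy data summarization is planned. Consequently, subset analyses will not be performed". SAP 8.9 leaves room for descriptive subgroups, which "may be performed for the procedure types obtained from the registry". Protocol 8.3 allows optional strata by procedure and baseline characteristics. None of these names site. SAP 12 refers to "tables which will be provided as a separate document". Section 13 (individual listings) appears in the SAP contents, but its text is not in the material supplied.

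On site size, the Protocol Summary gives "Up to 10 sites in the United States with a maximum enrollment of no more than 30% patients at each participating site". Protocol 4.3 states the base of that cap: "Each participating registry site will be allowed a maximum enrollment of no more than 30% patients from the total planned enrollment". SAP 4.1 describes an "interim analysis planned at 100 subjects to conduct safety and performance analysis for data submission toward CE mark application".

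**The concern.** An exact binomial interval treats patients as independent. Here they are grouped by centre. Imaging success is scored by the investigator, so rater and site go together, and Protocol 6.4 leaves catheter model, access, views and imaging sequence to the operator. Success rates may well differ between sites.

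The documents also invite a reading beyond the enrolled sites. Protocol 3.3 gives a representative sample of physicians as a reason for the multicentre design. Protocol 2.3 foresees filings outside the US, although all sites are in the US. Protocol 8.1 says of the sample size: "This sample size will provide the opportunity to make proper statistical inference for hypothesis generation". If the cap is 30% of 200, one site may supply 60 of the first 100 patients, and that is the data set meant for the CE mark application. A reader might then take the stated 95% as covering centres in general, with no by-site result in the SAP text to show whether one centre drives the estimate.

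**Working it through.** **Inputs from the documents.** Clopper-Pearson, two-sided, 95%; 100 patients at the interim analysis and up to 200 in all; up to 10 sites; cap 0.30 × 200 = 60 patients per site, which is 60/100 = 60% of the interim data if one site recruits early.

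**Assumed, because the documents give neither.** True success p of 90%, 95% or 98% (Protocol 2.2 cites technical success of 96.7% to 100% for ICE in appendage closure) and ICC of 0.01 to 0.05. The SD of true site rates is √(ICC × p × (1 − p)). At p = 90% this is √(0.01 × 0.09) = 3.0 points to √(0.05 × 0.09) = 6.7 points. At 95% it is 2.2 to 4.9 points, and at 98% it is 1.4 to 3.1 points.

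**Step 1: the SAP's own statement.** With independent patients, exact coverage is the sum of binomial probabilities over all counts whose interval contains p. For true rates of 85% to 97% it is 95.6% to 98.9% at n = 100 and 96.3% to 96.7% at n = 200. The claim of at least 95% is reproduced.

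**Step 2: enrolled sites with different rates.** Take the target as the enrolment-weighted mean p̄ of the enrolled sites' own rates. The variance of the total count is n p̄(1 − p̄) − Σ mᵢ(pᵢ − p̄)², which never exceeds the binomial variance.

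- One site of 60 at 97% and four of 10 at 80, 83, 87 and 90%: p̄ = (58.2 + 8.0 + 8.3 + 8.7 + 9.0)/100 = 92.2%. The binomial variance is 100 × 0.922 × 0.078 = 7.19. The actual variance is 1.746 + 1.600 + 1.411 + 1.131 + 0.900 = 6.79. Coverage is 96.8%.
- Ten sites of 20, evenly spaced from 85% to 99%: coverage is 96.6%.

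For this target the interval does not need a common success probability, and it is slightly conservative.

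**Step 3: sites as a sample from a wider population.** Site rates are drawn from a beta distribution with mean p and the stated ICC, patients are binomial within site, and coverage of p is computed exactly. The design effect is 1 + (Σmᵢ²/n − 1) × ICC. At ICC 0.05 it is 1 + 9 × 0.05 = 1.45 for ten sites of 10, 1 + 19 × 0.05 = 1.95 for ten of 20, and 1 + 39 × 0.05 = 2.95 for one of 60 plus four of 10.

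| Sites | ICC | p = 90% | p = 95% | p = 98% |
|---|---|---|---|---|
| n = 100, ten of 10 | 0.01 | 94.6% | 97.7% | 98.0% |
| | 0.02 | 93.6% | 97.2% | 97.5% |
| | 0.05 | 90.5% | 95.4% | 96.1% |
| n = 100, one of 60 and four of 10 | 0.01 | 91.3% | 95.8% | 96.4% |
| | 0.02 | 87.0% | 93.2% | 94.7% |
| | 0.05 | 76.6% | 86.8% | 92.0% |
| n = 200, ten of 20 | 0.01 | 94.9% | 95.0% | 94.4% |
| | 0.02 | 93.0% | 93.3% | 92.5% |
| | 0.05 | 87.3% | 88.1% | 87.0% |
| n = 200, three of 60, seven sharing 20 | 0.01 | 91.5% | 91.9% | 91.1% |
| | 0.05 | 73.3% | 75.7% | 75.3% |

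Coverage is uneven in p. With one site of 60 and p = 96% it is 92.8%, 89.4% and 81.6% at ICC 0.01, 0.02 and 0.05, below the values for 95% and 98%.

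**Step 4: would a clustered interval do better?** A Korn-Graubard interval with a t-correction for the number of sites was simulated (40,000 replicates).

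- Ten sites of 20, p = 95%: mean width 10.4 against 6.4 points for Clopper-Pearson at ICC 0.05, and 8.3 against 6.5 at ICC 0.01.
- Ten sites of 20, ICC 0.05: coverage 96.4%, 96.3% and 93.4% at p = 90, 95 and 98%, so it falls short even with balanced sites.
- One site of 60 and four of 10, ICC 0.05: about 92% at p = 90% and 95%.
- Two sites of 60 and 40: mean width 51 to 75 points over ICC 0.01 to 0.05, which is of no use.

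**The case for a change.** The strongest case is that the SAP chose to report intervals and justified them by a coverage guarantee, so it should state the condition for that guarantee, and that a by-site table costs almost nothing from data already held. The assumed ICC is no answer to this: because its size is unknown, a reader would want to see the sites.

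Part of this stands. The interval contains no between-site variation, the SAP does not say so, and read literally 8.2.3 excludes by-site success rates. If the results are carried to other centres, the intervals may be too narrow, and a dominant site makes that worse.

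The rest does not carry. The guarantee is correct for the binomial model that the SAP names. The pooling is open and prespecified. Protocol 8.1 limits its remark on inference to hypothesis generation and calls the outcomes exploratory, and Protocol 3.1 says that no specific claims are being validated. That readers could not judge the role of single sites is not established, because the table shells and the section 13 listings were not available. By-site rates alone could also mislead: Protocol 4.3 expects electrophysiology, appendage, valve and septal-defect cases, and site may be mixed up with procedure type.

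**Conclusion.** No change to the plan is needed. The Clopper-Pearson interval is valid and slightly conservative for the enrolled sites at their own mix, which is the only target that a pooled descriptive registry without hypothesis or performance goal clearly sets. No decision rule depends on its coverage.

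For a wider population of sites, coverage runs from 98% down to about 73% over the layouts and ICC values shown. The low values need a few large sites together with an ICC near 0.05. With ten equal sites at n = 100 and 95% or 98% success there is no shortfall, and at n = 200 with ten equal sites and ICC 0.01 coverage is 94.4% to 95.0%. The ICC, the success rates and the site split are all assumptions here.

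The possible alternatives do not correct an error. A caveat sentence would only record a known property of the method. A by-site table is an optional description and would need the procedure mix beside it. A clustered interval trades width for coverage that it does not always reach. Applying the cap to the first 100 patients would need a protocol amendment with IRB approval and could slow enrolment. Report authors can fill the gap by noting that the intervals treat patients as independent and by describing enrolment by site.
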